2.0 OBJECTIVES AND SCIENTIFIC AIMS

2.1 Primary Objective:

- To explore the therapeutic efficacy of buparlisib in patients with PCNSL and SCNSL as measured as progression free survival at 24 weeks (PFS24w)

2.2 Secondary Objectives:

- To explore the safety and tolerability of buparlisib in PCNSL and SCNSL patients by assessing the frequency and severity of adverse events
- To assess overall response rate (ORR) on MR imaging in patients with PCNSL and SCNSL receiving buparlisib
- To assess progression free survival at 12 weeks (PFS12w) and 48 weeks (PFS48w) in patients with PCNSL and SCNSL receiving buparlisib
- To assess the duration of response (DoR) and overall survival (OS) in patients with PCNSL and SCNSL receiving buparlisib
- To evaluate CSF pharmacokinetics of buparlisib by measuring drug concentration in serum and CSF samples

2.3 Exploratory Objectives:

- To correlate differences in drug response to PI3K pathway activation status through mutational and immunohistochemical analysis of PI3K pathway members such as but not limited to phospho-AKT, phospho-S6, phospho-4EBP1
- To characterize mutational abnormalities in paired tumor/germline DNA in PCNSL/SCNSL patients and correlated with drug response

- To correlated changes on ADC/DWI/perfusion MRI imaging to drug response
- To assess neurologic functioning using the Neurologic Assessment in Neuro-Oncology (NANO)

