3.0 BACKGROUND AND RATIONALE

3.1 Primary central nervous system lymphoma (PCNSL)

PCNSL is an aggressive subtype of diffuse large B-cell lymphoma (DLBCL) with increasing incidence over the last decade (Deangelis, 2006). PCNSL usually develops in the brain but can also involve other compartments of the CNS including spinal cord, meninges, cerebrospinal fluid, and eyes. Compared to systemic DLBCL, PCNSL has a poorer prognosis (Ferreri 2011) with a cure rate of around 20-30% (Reni, Ferreri et al. 1997; Gavrilovic, Hormigo et al. 2006). Prognosis is especially poor for patients over age of 60 and patients with relapsed/refractory disease. The management of this disease poses a difficult challenge in neuro-oncology. Median survival for patients with progressive disease without treatment is two months. Unfortunately, the optimal salvage regimen is not known and only a few prospective clinical trials have addressed this patient population. In contrast to other CNS malignancies, patients with PCNSL are mainly treated with conventional methotrexate-based chemotherapy and targeted agents have not been introduced into the treatment regimen of PCNSL. Even in patients with treatment resistant PCNSL, further chemotherapy or radiation is used. Targeting molecular abnormalities has not been advanced in PCNSL mainly because the molecular pathogenesis of PCNSL remains still largely unknown due to the relative rarity of this disease and the fact that tumor tissue is usually collected in only small quantities for diagnostic purposes. In systemic lymphoma, gene expressions profiling has identified two major subgroups: germinal center type and activated B cell (ABC) the latter being associated with a poorer clinical prognosis (Alizadeh et al., 2000) but ABC DLBCL cell lines have shown to respond remarkably well to targeted inhibition of the phosphatidylinositol-3-kinase (PI3K) pathway (Kloo, 2010). More than 95% of PCNSL cases are of the ABC/non-germinal center subtype (Camilleri-Broet, Criniere 2006). Therefore, the use of PI3K inhibitors could be promising in PCNSL, particularly in patients that have failed conventional methotrexate-containing chemotherapy regimens.

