3.2 Secondary CNS Lymphoma (SCNSL)

SCNSL represents CNS involvement through direct invasion by a systemic non-Hodgkin lymphoma. SCNSL incidence has increased with more effective first-line therapy of systemic DLBCL. SCNSL most commonly presents with concurrent systemic progression of lymphoma and carries a poor prognosis with a median survival of 1-5 months (Grier and Batchelor, 2005). Involvement of the CNS may include the brain and leptomeninges. Like PCNSL, SCNSL therapy is challenging and usually involves methotrexate-based chemotherapy. For patients failing chemotherapy, palliative radiation can be offered but prognosis is dismal.

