4.1.1 Rationale for the study design

An open label, single arm, phase II study has been selected to explore the efficacy and safety of buparlisib in patients with relapsed/refractory PCNSL and relapsed/refractory SCNSL. Twenty-one patients will be enrolled of which at least 10 will have relapsed/refractory PCNSL.

No clear data exist on the effect of targeted therapy in either PCNSL or SCNSL. Additionally, no clear data exist that activation of the PI3K pathway in PCNSL or SCNSL is predictive for response to a PI3K inhibitor. Thus, enrollment of patients with activated as well as non-activated PI3K pathway is considered appropriate.

In the absence of a comparative arm but based on historical data, PFS24w is considered an appropriate primary endpoint to objectively measure anti-tumor activity.

A single arm study will be performed due to lack of approved agents as well as small patient population.

The protocol specific assessments, treatment and follow-up are consistent with a standard procedures applied in this disease setting.

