Frequencies of toxicities will be summarized based on the Common Toxicity Criteria version 4.0. Adverse events that occur will be reported for and described in terms of incidence and severity. Objective response rate (defined as proportion of patients who achieve a complete and partial response among all patients) will be estimated along with a 95% confidence interval. For patients who respond to treatment (complete or partial response), duration of response will be calculated from the date of response to the date of progression of disease. Patients still responding at date of last follow-up will be censored. Overall survival will be calculated as the time from the start of treatment to the date of death or last follow-up. Overall survival and duration of response will be calculated using Kaplan-Meier methodology.

Pharmacokinetic parameters including half-life, C_{max} , AUC, volume of distribution, and clearance will be determined using non-compartmental methods via WinNonlin (Pharsight, Mountain View, CA). Standard descriptive statistics (mean, standard deviation, median, range) will be presented on all parameters for both serum and CSF samples.

Mutational abnormalities (mutant or not) will be assessed for the following genes: A20, CARD11, CD79B, PIK3CA, PIK3CD and MYD88. Additionally, the phosphorylation status of the following members of the PI3K pathway will be assessed through immunohistochemical staining (activated or not activated). Both, mutational abnormalities as well as immunohistochemical status will be cross tabulated with patient outcomes such as PFS24w and ORR. Associations will be assessed using Fishers exact test. For patients who receive MR spectroscopy peak values will be described and graphically presented through course of treatment. Perfusion data (ADC value categorized as high versus low) will be correlated with patient outcome if data permit.

The evaluation of NANO will be measured by the distribution of change from baseline in the level of function score for each domain.

It is anticipated that 1-2 patients per month will be accrued to this study and the study will be completed within 2 years. Accrual is limited to 10 patients with SCNSL and 11 patients with PCNSL.

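### Section 14 tests mutation and IHC markers against outcome with no split between PCNSL and SCNSL, so a disease difference could pass for, or hide, a marker effect if both marker and outcome differ by disease

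*Combined protocol and SAP*

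**What the plan says.** The exploratory aim in Section 2.3 takes the two diseases together: "To characterize mutational abnormalities in paired tumor/germline DNA in PCNSL/SCNSL patients and correlated with drug response". A companion aim relates drug response to PI3K pathway activation.

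Section 14 gives the analysis. "Mutational abnormalities (mutant or not) will be assessed for the following genes: A20, CARD11, CD79B, PIK3CA, PIK3CD and MYD88". IHC status is coded as activated or not; Section 10.5.1 names pAKT, pS6 and p4EBP1. Then "Both, mutational abnormalities as well as immunohistochemical status will be cross tabulated with patient outcomes such as PFS24w and ORR", and "Associations will be assessed using Fishers exact test". This means one two-by-two table for each marker and outcome. No significance level, stratification or adjustment is stated.

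The same section fixes the case mix: "Accrual is limited to 10 patients with SCNSL and 11 patients with PCNSL". Section 4.1.1 is compatible with this: "Twenty-one patients will be enrolled of which at least 10 will have relapsed/refractory PCNSL". Sections 10.5.1 and 10.5.2 say only that marker results will be correlated with response. Pooling is therefore inferred from silence, but it is the plain reading, since nothing in the plan splits an efficacy or marker analysis by disease.

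**The concern.** The exploratory question is whether pathway activation or mutation goes with response to buparlisib. In a near-even mix of two diseases, a pooled table answers that question only if disease type is unrelated to the marker or unrelated to the outcome. If it is related to both, a marker that is commoner in the disease with better outcomes looks favourable even when it does nothing within either disease. A marker that is commoner in the disease with worse outcomes can have a real effect hidden. Section 4.1.1 says there are no clear data that activation predicts response, so a pooled association from this trial could be taken as early evidence of prediction when it only marks the diagnosis.

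**Working it through.** **The plan's own figure.** Section 14 computes nothing for the marker tests. Its only calculated figures are the exact intervals in Table 14, and these reproduce: 12/21 gives 34.02% to 78.18%. The marker analysis does not enter the 12-of-21 rule.

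**Inputs.** From the documents: 11 PCNSL, 10 SCNSL, binary markers, binary outcomes, Fisher's exact test. Assumed: two-sided 5% level, and marker and outcome rates by disease. The documents give no SCNSL marker rate and no PFS24w or ORR by disease.

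**Expected pooled association with no marker effect within disease.** Let m1, m2 be the marker prevalence and p1, p2 the outcome rate in PCNSL and SCNSL.

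- Rate if marker-positive = (11·m1·p1 + 10·m2·p2) / (11·m1 + 10·m2)
- Rate if marker-negative = (11·(1−m1)·p1 + 10·(1−m2)·p2) / (11·(1−m1) + 10·(1−m2))

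Marker 70/30, outcome 50/20:
- Positive: (3.85 + 0.60) / (7.7 + 3.0) = 4.45/10.7 = 41.6%
- Negative: (1.65 + 1.40) / (3.3 + 7.0) = 3.05/10.3 = 29.6%
- Odds ratio: (4.45/6.25) / (3.05/7.25) = 1.69

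Marker 80/20, outcome 60/10:
- Positive: (5.28 + 0.20) / (8.8 + 2.0) = 5.48/10.8 = 50.7%
- Negative: (1.32 + 0.80) / (2.2 + 8.0) = 2.12/10.2 = 20.8%
- Odds ratio: (5.48/5.32) / (2.12/8.08) = 3.93

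The true odds ratio within each disease is 1 in both cases.

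**False-positive rate.** The pooled Fisher test was compared with an exact test stratified by disease. The stratified test conditions on the margins within each disease, so the total of marker-positive successes follows the convolution of two hypergeometric distributions. The two-sided p-value sums the probabilities no larger than the observed one. There were 40,000 simulated trials per row (Monte Carlo standard error at most 0.23 points).

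| Marker % PCNSL/SCNSL | Outcome % PCNSL/SCNSL | Apparent OR | Pooled Fisher | Stratified exact |
|---|---|---|---|---|
| 50/50 | 34/34 | 1.0 | 2.6% | 2.4% |
| 50/50 | 50/20 | 1.0 | 2.7% | 2.3% |
| 70/30 | 34/34 | 1.0 | 2.6% | 2.2% |
| 60/40 | 50/20 | 1.3 | 3.4% | 2.3% |
| 70/30 | 50/20 | 1.7 | 5.2% | 1.9% |
| 80/20 | 50/20 | 2.2 | 8.4% | 1.4% |
| 70/30 | 60/10 | 2.4 | 10.0% | 1.4% |
| 80/20 | 60/10 | 3.9 | 21.2% | 1.2% |

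A still wider outcome gap, 80/20 with 70/10, gives 30.0% against 1.1% (odds ratio 4.8).

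**Anchored to the one marker rate in the documents.** Section 3.7 reports p4EBP1 positivity in 79.1% of 138 PCNSL samples. The SCNSL and outcome rates remain assumed (30,000 trials per row).

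| Marker % | Outcome % | Pooled Fisher | Stratified exact |
|---|---|---|---|
| 79/79 | 45/20 | 1.8% | 1.4% |
| 79/60 | 45/20 | 2.2% | 1.7% |
| 79/50 | 50/20 | 3.4% | 1.8% |
| 79/40 | 50/20 | 4.4% | 1.8% |
| 30/10 (a rarer marker, not anchored) | 50/20 | 3.5% | 1.5% |

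A rejection rate under 5% does not mean the estimate is unbiased. For 79/40 with 50/20 the expected rates are 5.145/12.69 = 40.5% and 2.355/8.31 = 28.3%, an apparent odds ratio of 1.7.

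**Power at an assumed within-disease odds ratio of 8 (pooled v stratified).** Marker balanced across diseases: 48.3% v 44.6%. Marker differs by disease but outcome does not: 48.2% v 36.8%. Marker commoner in the disease with worse outcomes: 22.4% v 29.2%.

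**The case against.** A reader might infer that the protocol's background already ties disease type to both sides of the table. It does not.

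- **Marker side.** Section 3.1 says "More than 95% of PCNSL cases are of the ABC/non-germinal center subtype", while systemic lymphoma falls into two subgroups. But cell of origin is not among the markers tested in Section 14, and no section gives a subtype, mutation or IHC rate for SCNSL patients. The only SCNSL marker data point the other way: Section 3.7 reports raised p4EBP1 and pS6 in all examined xenograft models, from a set of 9 PCNSL and 3 SCNSL.
- **Outcome side.** Section 3.2 says SCNSL "carries a poor prognosis with a median survival of 1-5 months", against OS of 4 to 26 months in the PCNSL series of Table 1. Those series are treated patients. Section 3.1 gives two months for progressive PCNSL without treatment, which lies inside 1 to 5 months. The SCNSL figure describes a population that most often has concurrent systemic progression. Section 6.2 requires systemic disease to have resolved, and Section 6.1 requires life expectancy above three months. Survival is also neither of the two named outcomes.

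The size is also easily overstated. If only one side differs, the pooled test stays at 2.6 to 2.7%. Fisher's test is conservative at 21 patients, so even gaps of 40 points in the marker and 30 points in outcome bring it only to about 5%. Replacing it outright would cost about 3 to 11 points of power when there is no confounding. Finally, the aim is exploratory, with no decision attached.

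All of this stands. It limits the size, the priority and the remedy. It does not remove the gap: the plan has no step that would show whether an association holds within each disease.

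**Conclusion.** The concern holds as a conditional one. Section 14 plans marker tests over two diseases in near-equal numbers with no split by disease. If marker prevalence and outcome both differ by disease, a disease difference can appear as a marker effect or hide one. The documents do not establish that both differ, so the actual bias is unknown.

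Under assumed rates, pooled null rejection is about 3 to 5% for moderate differences and about 21% for extreme ones (30% at the widest gap tried), against about 2% or less when stratified. The apparent odds ratio is about 1.7 at 70/30 with 50/20 and 3.9 at 80/20 with 60/10. The distortion of the estimate matters more than the rejection rate, because it is present even when the test stays below 5%. These figures rest on a two-sided 5% level, full 11 + 10 accrual and a result for every patient. Priority is low: the analysis is exploratory and the primary rule is unaffected.

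**What to change.** In Section 14, keep the Fisher test and add four things:

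1. Show every marker-by-outcome table separately for PCNSL and SCNSL as well as combined.
2. Report an exact test stratified by disease (exact conditional Mantel-Haenszel, or permutation within disease) beside the pooled result.
3. Label all marker results descriptive.
4. State that a pooled association will not be read as predictive unless its direction is the same within each disease.

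The cost is a few sentences and a little programming. Disease type must already be recorded to apply the accrual caps, so no extra patients or data are needed. With strata of 11 and 10 the stratified test has low power and rare mutations will tell little, which is why it should stand beside the pooled test and not replace it.

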12.8 Progression-free survival (PFS)

Progression-free survival (PFS) is defined as the time from the date of treatment start to the date of the first documented PD or death due to any cause. If a patient is not known to have progressed or died at the date of the analysis cut-off or when he/she receives any further anti-cancer therapy, PFS is censored at the time of the last tumor assessment before the cut-off date and before the anti-cancer therapy date. PFS will be based on the investigator's assessment of MRI, CSF studies and clinical presentation.

PFS will be described using Kaplan-Meier curves with appropriate summary statistics. Additionally, we will report PFS at 12 weeks (PFS12w), PFS at 24 weeks (PFS24w) and at 48 weeks (PFS48w).

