14.0 BIOSTATISTICS

As outlined in Table 1 Section 3, prior trials in patients with recurrent PCNSL have observed PFS6m of 35-45% with conventional chemotherapy regimens. The primary objective of this phase II study is to assess the efficacy of the targeted therapy buparlisib. PFS24w rate of patients receiving buparlisib will be estimated along with a 95% confidence interval. Progression-free survival at 24 weeks (PFS24w) is defined as the percentage of patients that have not developed progression of disease or died without progression at 24 weeks from the start of treatment. All patients will be followed for 6 months.

Twenty-one patients will be entered in this trial with an anticipated accrual rate of 1-2/months. The therapy will be considered worth pursuing if ≥ 12 out of 21 participants are progression free at 6 months (lower bound of the 95% confidence interval exceeds 34%, the approximate PFS24w rate with conventional chemotherapy).

Based on an accrual of 21 participants, two-sided 95% binominal confidence intervals for a range of overall response rate are as follows:

Table 14: Two-sided 95% binominal confidence intervals

Number of participants with overall response:		6	8	10	12	14	16
Point estimate of overall response rate:		29%	38%	48%	57%	67%	76%
Two-sided 95% confidence interval (exact binominal):	lower	11.28%	18.11%	25.71%	34.02%	43.03%	52.83%
	upper	52.18%	61.56%	70.22%	78.18%	85.41%	91.78%

In the unlikely event a patient is lost to follow-up before assessment of the primary endpoint he or she will be considered an event in the analysis of the primary endpoint.

In addition to PFS24w, we will assess progression-free survival at 12 weeks and 48 weeks (PFS12w and PFS48w). PFS12w/PFS48w is defined as the percentage of patients that have not developed progression of disease or died without progression at 3/12 months from the start of treatment. PFS12w and PFS48w rates of patients receiving buparlisib will be estimated along with a 95% confidence interval. The PFS12w will be assessed based on the

MEMORIAL SLOAN-KETTERING CANCER CENTER IRB PROTOCOL

IRB#: 14-177 A(5)

imaging and/or CSF assessment at day 1 cycle 3. PFS24w will be based on the imaging and/or CSF assessment at day 1 cycle 6, and PFS48w on imaging and/or CSF assessment at day 1 cycle 12.

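### Marker associations with PFS are tested only on yes/no PFS24w with Fisher's exact test; a log-rank test on the PFS times already collected would be more efficient

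*Combined protocol and SAP*

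**What the plan says.** The marker aims are exploratory. Section 2.3 sets out "To correlate differences in drug response to PI3K pathway activation status", and a companion aim does the same for mutations. Section 14.0 fixes the coding: "Mutational abnormalities (mutant or not) will be assessed for the following genes: A20, CARD11, CD79B, PIK3CA, PIK3CD and MYD88", with immunohistochemical status recorded as activated or not. It continues: "Both, mutational abnormalities as well as immunohistochemical status will be cross tabulated with patient outcomes such as PFS24w and ORR". The only test named is in the next sentence: "Associations will be assessed using Fishers exact test". Significance level, sidedness, effect size, marker prevalence and power are not given for these tests.

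PFS is also available as a time. Section 12.8 opens with "Progression-free survival (PFS) is defined as the time from the date of treatment start", runs it to first progression or death with censoring rules, and adds that "PFS will be described using Kaplan-Meier curves with appropriate summary statistics". That description covers all patients together; no log-rank, Cox or other time-to-event comparison by marker appears. Table 6 schedules imaging on day 1 of odd 28-day cycles from cycle 3, so every 8 weeks. PFS48w is a secondary objective in section 2.2 and is estimated in section 14.0. On size, section 14.0 says "Twenty-one patients will be entered in this trial with an anticipated accrual rate of 1-2/months".

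**The concern.** Reducing PFS to progression-free or not at 24 weeks treats progression at week 8 like progression at week 24, and progression at week 32 like no progression by week 48. This applies even where the marker is truly binary, such as a mutation. Fisher's test on a table of 21 also rejects well below its nominal 5% under the null. Both features reduce the chance of seeing a real association in tissue studies that section 10.5 makes mandatory for every participant.

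The binary outcome also has loose edges. Section 14.0 ties PFS24w to day 1 of cycle 6, which is 5 × 28 = 140 days, or week 20, and Table 6 schedules no imaging in even cycles. Section 14.0 counts a patient lost before the primary assessment as an event, whereas section 12.8 censors at the last assessment. The plan does not say which coding the marker tables use. A log-rank test on PFS as defined in 12.8 needs neither rule.

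Only the exploratory marker analyses are at stake. The primary endpoint and its decision rule are unaffected.

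**Working it through.** **The plan's own figure.** Section 14.0 states no power or effect for the marker tests, so there is nothing there to reproduce. Its one statistical figure is the exact interval for the decision rule. For 12/21 = 57%, the Clopper-Pearson limits are the 0.025 quantile of Beta(12, 10) and the 0.975 quantile of Beta(13, 9). These give 34.02% and 78.18%, as in Table 14. This confirms n = 21 but does not bear on the markers.

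**Inputs.** From the documents: n = 21, binary markers, an 8-weekly assessment grid. Assumed: exponential PFS, proportional hazards, two-sided 5%, and the splits, base rates and hazard ratios (HR) shown. If S is the marker-negative PFS24w, the marker-positive value is S^HR; for example 0.30^0.3 ≈ 0.70 and 0.30^0.5 ≈ 0.55.

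**Power, Fisher on PFS24w against permutation log-rank on PFS time** (1,500 simulated trials per row):

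| Marker +/− | S | HR | PFS to week | Fisher | Log-rank | Gain |
|---|---|---|---|---|---|---|
| 8/13 | 15% | 0.4 | 48 | 28% | 46% | 18 |
| 8/13 | 15% | 0.3 | 48 | 47% | 68% | 21 |
| 8/13 | 30% | 0.4 | 48 | 22% | 41% | 19 |
| 8/13 | 30% | 0.3 | 48 | 31% | 59% | 28 |
| 10/11 | 30% | 0.3 | 48 | 37% | 61% | 24 |
| 5/16 | 30% | 0.3 | 48 | 32% | 55% | 23 |
| 8/13 | 15% | 0.5 | 48 | 20% | 26% | 6 |
| 8/13 | 30% | 0.5 | 48 | 13% | 23% | 10 |
| 8/13 | 15% | 0.4 | 24 | 31% | 32% | 1 |
| 8/13 | 15% | 0.3 | 24 | 44% | 50% | 6 |
| 8/13 | 30% | 0.4 | 24 | 23% | 28% | 5 |
| 8/13 | 30% | 0.3 | 24 | 33% | 38% | 5 |

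Separate runs at 8/13 and 13/8 gave gains of about 14-28 points at HR 0.3-0.4 to week 48, about 8-13 at HR 0.5, and about 4-13 with PFS cut at 24 weeks. Runs do not agree exactly: one put the first row at 30% against 41%, a gain of 11. The gain depends on whether the permuted statistic is observed minus expected events or the standardised chi-square.

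**Very uneven splits.** The only marker prevalence in the documents is 79.1% for phospho-4EBP1 (section 3.7). That gives 0.791 × 21 = 16.6, so about 17 against 4. At an overall PFS24w of 45% and HR 0.25-0.5, the permutation log-rank gained from 0 to about 22 points, depending on follow-up. With 4 positive and 17 negative, gains reached 62.4 − 21.2 = 41 points at HR 0.25 with long follow-up. The ranges above should not be carried to such markers.

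**Size.** Under no effect, Fisher rejects about 2-3% of the time and the permutation log-rank about 4-5%. At 10/11, a mid-p version of Fisher's test recovers about 2-3 points of power, so a small part of the gap is conservatism and the rest is lost time information.

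**Multiplicity.** Six genes (section 14.0) and three named stains (section 10.5.1) make nine markers. Treating them as independent and unadjusted, the chance of at least one false positive is 1 − (1 − a)^9. At a = 0.026 (Fisher) this is 21%; at a = 0.052 (log-rank), both from one null run, it is 38%.

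**The case against.** The best defence is that nothing here is wrong. The aims ask about drug response, for which ORR is the direct measure and Fisher's exact test is appropriate. PFS24w is the primary endpoint, and testing markers against it is coherent and valid. Section 14.0 offers the two outcomes only as examples, and section 12.8 already plans Kaplan-Meier curves, so nothing forbids a display by marker. Most of the gain needs scans beyond week 24. Section 14.0 promises 6 months of follow-up for all, section 13.0 specifies no imaging after removal, and section 12.8 censors at further anti-cancer therapy. Even the better test has only 41-46% power at HR 0.4.

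Most of this stands, and it limits the point to efficiency. It does not remove it. Open wording about outcomes does not supply a time-to-event test, since the one test named requires a categorical outcome. PFS48w is a stated objective, so follow-up past 24 weeks is intended. The gain is also not bought with a size above 5%.

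A reader might infer that the plan loses 15 to 30 points of power whatever the circumstances, or that Fisher's test is an error. The documents support neither. They give no effect size or mutation prevalence, the gain falls to a few points under shorter follow-up or smaller effects, and the planned test controls its error rate.

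**Conclusion.** The point holds as a minor inefficiency in an exploratory analysis. For PFS, the only test named uses a 24-week dichotomy and leaves the collected times unused by marker. At splits near 8/13, the gain from a permutation log-rank test is about 14-28 points at HR 0.3-0.4 with PFS followed to week 48. It is near zero to about 13 points at HR 0.5 or with PFS cut at 24 weeks. These figures rest on assumed effects, exponential PFS with proportional hazards, and complete 8-weekly assessments. Confidence is high on the direction and moderate on the size. Neither test makes 21 patients adequate for anything but a very large effect.

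**What to change.** In section 14.0, split the marker analysis by outcome:

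- **PFS:** test each marker with a permutation log-rank test on PFS time as defined in section 12.8, and report a hazard ratio with 95% CI (for example from Firth-penalised Cox regression, given few events per group). State the significance level, the sidedness and the permutation statistic in advance; the standardised log-rank chi-square is the steadier choice for uneven splits.
- **ORR:** keep Fisher's exact test.
- **PFS24w by marker:** show the cross-tabulation descriptively.

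State how many markers are tested, that no multiplicity adjustment is made, and that results are hypothesis-generating. That label matters more after the change, because a test nearer its nominal 5% level yields more chance positives over about nine markers.

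The cost is a few sentences of SAP text and a few lines of code. No new data, visits or patients are needed, and the primary analysis is untouched.
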